20.1.1. ALL AEs

Incidence of TEAEs will be presented by both by Preferred Term (PT) and by System Organ Class (SOC) and Preferred Term (PT) by decreasing percentages of PT.

20.1.1.1. Severity

Severity is classed as mild / moderate / severe (increasing severity). TEAEs starting after the first dose of study medication with a missing severity will be classified as severe. If a participant reports a TEAE more than once within that SOC / PT, the AE with the worst-case severity will be used in the corresponding severity summaries. TEAE by maximum severity will be summarized by decreasing percentages of PT.

20.1.1.2. Relationship to Study Medication

Relationship, as indicated by the Investigator, is classed as No, Yes. A "related" TEAE is defined as a TEAE with a relationship to study medication as 'Yes'. TEAEs with a missing relationship to study medication will be regarded as Yes related to study medication. If a participant reports the same AE more than once within that SOC / PT, the AE with the worst-case relationship (i.e. Yes) to study medication will be used in the corresponding relationship summaries and will be presented by decreasing percentages of PT. A listing of TEAE related to

Document: **CCI**

Author: **PPD**

Version Number:

3.0

Version Date:

19May2023

CCI

non-study drug treatment will be presented as well.

20.1.1.1. Adverse Events by Outcome

A summary of TEAE by outcome and PT will be presented.

20.1.1.2. Serious Adverse Events

Serious adverse events (SAEs) are those events recorded as "Serious" on the Adverse Events page of the electronic case report form (eCRF). A summary of all SAEs and serious TEAEs by PT will be prepared and will present the following will be provided:

- the number of participants at risk of an event
- the number of participants who experienced each event term
- the number of events experienced.

20.1.1.3. Other Adverse Events

An AE is considered in the "Other" category if it is both a TEAE and is not serious. For "Other" AE, for each term and treatment group, the following will be provided:

- the number of participants at risk of an event
- the number of participants who experienced each event term
- the number of events experienced.

20.1.1.4. TEAEs Leading to Discontinuation of Study Intervention

TEAEs leading to permanent discontinuation of study medication will be identified by using AE action as "Drug Withdrawn". Summaries of incidence rates (frequencies and percentages) by PT will be prepared.

20.1.1.5. Adverse Events Leading to Study Discontinuation

All AEs leading to discontinuation from the study (from any of the following Study Disposition forms: DS_HEP, DS_SDWOV, DS_SF, DS_STUDY) will be summarized.

Document: **CCI**

Author: **PPD**

Version Number:

3.0

Version Date:

19May2023

CCI

20.1.1.1. Adverse Events Leading to Death

All TEAEs leading to death will be summarized and listed.

20.1.1.2. Adverse Events Related to Injection Sites

TEAEs related to injection sites will be defined using terms from the MedDRA High Level Term “Injection Site Reactions”.

The number and percentage of participants with TEAEs related to injection sites, SAEs related to injection sites, and AEs related to injection sites resulting in study drug discontinuation will be summarized using MedDRA PT. Events will be ordered by decreasing frequency within PT.

The number and percentage of participants with TEAEs related to injection sites by maximum severity will be summarized by treatment groups using MedDRA PT. For each participant and AEs related to injection sites, the maximum severity for the MedDRA level being displayed (PT) is the maximum post-baseline severity observed from all associated LLTs mapping to that MedDRA level.

The number and percentage of participants with TEAEs related to injection sites by timing will be summarized using MedDRA preferred terms ordered by decreasing frequency. Note the timing of AEs related to injection sites is collected through eCRF and categorized into the following categories:

- Occurs DURING study drug administration
- within 30 minutes of end of study drug administration
- >30 minutes and up to 6 hours from end of study drug administration
- >6 Hours and up to 24 Hours from end of study drug administration
- >24 Hours and Up to 14 Days from end of study drug administration
- >14 Days from end of study drug administration
- Unknown

20.1.1. ADVERSE EVENTS OF SPECIAL INTEREST

Not applicable.

Document: **CCI**

Author: **PPD**

Version Number:

3.0

Version Date:

19May2023

CCI

20.1.2. CTC GRADING FOR ADVERSE EVENTS

Not applicable.

20.2. LABORATORY EVALUATIONS

Results from the central laboratory will be included in the reporting of this study for Hematology, Clinical Chemistry and Urinalysis. A list of laboratory assessments to be included in the outputs is included in the protocol, Sections 10.4 and 10.5. Presentations will use SI Units. The incidence rates of participants with treatment emergent abnormal, high, or low laboratory values based on the reference ranges at any time post-baseline will be assessed using Fisher's exact test for each laboratory test.

Participants will be defined as having a treatment emergent low value if they have normal or high values at all predose/baseline visits, followed by a value below the lower reference limit at any post-baseline visit. Participants with normal or high values at all predose/baseline visits (no low values) will be included in the analysis of treatment emergent low laboratory values. Participants will be defined as having a treatment emergent high value if they have normal or low values all predose/baseline visits, followed by a value above the upper reference limit at any post-baseline visit. Participants with normal or low values all predose/baseline visits (no high values) will be included in the analysis of treatment emergent high laboratory values. For analyses simply classified as normal or abnormal, participants will be defined as having a treatment emergent abnormal value if they have normal values all predose/baseline visits, followed by an abnormal value at any post-baseline visit. Participants with normal values all predose/baseline visits will be included in the analysis of treatment emergent abnormal laboratory values.

The incidence of participants with the following elevations in hepatic laboratory tests at any time post-baseline will also be summarized and compared between treatment groups using Fisher's exact test. A listing of participants with any of these elevations will be produced and will include all LFT parameters and visits.

- The number and percentage of participants with an alanine aminotransferase (ALT) or aspartate aminotransferase (AST) measurement greater than or equal to 1 time (1X), 3 times (3x), 5 times (5x), 10 times (10x), and 20 times (20x) the performing lab upper limit of normal (ULN) during the treatment period will be summarized for all participants with a post-baseline value.

Document: **CCI**

Author: **PPD**

Version Number:

3.0

Version Date:

19May2023

CCI

- The number and percentage of participants with an alkaline phosphatase (ALP) measurement greater than or equal to 2 times (2x) and 3 times (3x), the performing lab ULN during the treatment period will be summarized for all participants with a post-baseline value.
- The number and percentage of participants with a total bilirubin (TBIL) measurement greater than or equal to 2 times (2x), 5 times (5x), and 8 times (8x) the performing lab ULN during the treatment period will be summarized for all participants with a post-baseline value.
- The number and percentage of participants with a direct bilirubin (BILDIR) measurement greater than or equal to 2 times (2x) and 5 times (5x) the performing lab ULN during the treatment period will be summarized for all participants with a post-baseline value.
- The number and percentage of participants with an international normalized ratio (INR) measurement greater than or equal to 1.5 times (1.5x), 3 times (3x), and 5 times (5x) the performing lab ULN during the treatment period will be summarized for all participants with a post-baseline value.
- The number and percentage of participants with gamma glutamyl transferase (GGT) measurement greater than or equal to 2 times (2x) the performing lab ULN during the treatment period will be summarized for all participants with a post-baseline value.

Additional Analyses:

Document: CCI

Author: PPD

Version Number:

3.0

Version Date:

19May2023

CCI

Treatment-Emergent Potentially Drug-Related Hepatic Disorders	
Potentially drug-related hepatic disorders are defined using a custom query based on the following SMQs:
 
 • Broad and narrow terms in the Liver-related investigations, signs and symptoms SMQ (20000008) • Broad and narrow terms in the Cholestasis and jaundice of hepatic origin SMQ (20000009) • Broad and narrow terms in the Hepatitis non-infections SMQ (20000010) • Broad and narrow terms in the Hepatic failure, fibrosis and cirrhosis and other liver damage SMQ (20000013) • Narrow terms in the Liver-related coagulation and bleeding disturbances SMQ (20000015) 
These SMQs are a subset of the sub-SMQs comprising the full Hepatic Disorders SMQ. Only the sub-SMQs considered applicable to capturing potentially drug-related hepatic disorders are included.
 
The percentage of study participants with any one of the MedDRA preferred terms from any of the SMQs will be summarized in addition to the percentages for each MedDRA preferred term.

Potentially Drug-Related Hepatic Disorders That Led to Permanent Study Treatment Discontinuation	
The percentages of study participants with potentially drug-related hepatic disorders that led to permanent discontinuation of study drug will be summarized only if there is a sufficient number to warrant a summary.

Hepatocellular Drug-Induced Liver Injury Screening Plot (TBL vs ALT or AST)	
Each participant's data is plotted based on their maximum postbaseline TBL (y-axis) and transaminase (ALT or AST, whichever is higher), regardless of the time between the two maximum values. Dashed lines represent TBL and transaminase cut-offs of 2X ULN and 3X ULN, respectively. A potential Hy's law case is circled and is defined as having a maximum postbaseline TBL equal to or exceeding 2X ULN within 30 days after maximum postbaseline ALT or AST equal to or exceeding 3X ULN, without cholestasis (defined as ALP less than 2X ULN).

Hepatocellular Drug-Induced Liver Injury Screening Table	
The percentages of study participants falling in each of the three relevant quadrants of the plot (right upper, left upper, right lower) will be summarized in a table.

Cholestatic Drug-Induced Liver Injury Screening Plot (TBL vs ALP)	
Each participant's data is plotted based on their maximum postbaseline TBL (y-axis) and ALP (x-axis), regardless of the time between the two maximum values. Dashed lines represent TBL and ALP cut-offs of 2X ULN and 3X ULN, respectively. A potential cholestatic liver injury case is circled and is defined as having a maximum postbaseline TBL equal to or exceeding 2X ULN within 30 days after maximum postbaseline ALP equal to or exceeding 3X ULN.

Document: CCI

Author: PPD

Version Number: 3.0

Version Date: 19May2023

Cholestatic Drug-Induced Liver Injury Screening Table	The percentages of study participants falling in each of the three relevant quadrants of the plot (right upper, left upper, right lower) will be summarized in a table.
List of Participants With Potential Hepatocellular Drug-Induced Liver Injury	
Includes participants falling in the right upper quadrant in the Hepatocellular Drug-Induced Liver Injury Screening plot
 
Variables to include are unique subject ID, age, sex, race, actual treatment (at first ALT/AST elevation), max AST, max ALT, max ALP, max TBL

List of Participants With Potential Cholestatic Drug-Induced Liver Injury	
Includes participants falling in the right upper quadrant in the Cholestatic Drug-Induced Liver Injury Screening plot
 
Variables to include are unique subject ID, age, sex, race, actual treatment (at first ALP elevation), max AST, max ALT, max ALP, max TBL

Participant profiles	
Participant profiles will be created for participants meeting criteria for a comprehensive hepatic evaluation (as defined in the protocol).
 
Participant profiles will include demographics, disposition, information collected on the hepatic safety CRFs (where applicable) and a display of study drug exposure, adverse events, medications, blood pressure, heart rate, and the liver -related measurements over time.
 
The review for these study participants include which treatment the participant was taking over time, the changes in hepatic labs over time, and the temporal association with potential causes. The review of participant profiles will also include the identification of any potential Hy's law case or potential cholestatic liver injury case that could have been missed by focusing only on the maximum values when determining 30-day time associations.

All laboratory data will be listed.

20.2.1. LABORATORY SPECIFIC DERIVATIONS

Quantitative laboratory measurements reported as “<X”, i.e. below the lower limit of quantification (BLQ), or “>X”, i.e. above the upper limit of quantification (ULQ), will be converted to X for the purpose of quantitative summaries, but will be presented as recorded, i.e. as “<X” or “>X” in the listings.

20.3. VITAL SIGNS

Vital signs include body temperature, blood pressure, and pulse. Blood pressure and pulse will be measured in triplicate in the sitting position after the participant has rested for at least 5

Document: CCI

Author: PPD

Version Number:

3.0

Version Date:

19May2023

CCI

minutes, and before collection of blood samples and dosing (if dosing is on the same day), according to the SoA, and following the study-specific recommendations included in the Reference Manual for the study.

The baseline criteria for determining treatment-emergent vital sign abnormalities are:

- Participants will be defined as having a treatment-emergent low value if they have all normal or high values at all predose/baseline visits, followed by a value below the lower reference limit at any post-baseline visit. Participants with all normal or high values at all predose/baseline visits (no low values) will be included in the analysis of treatment-emergent low values.
- Participants will be defined as having a treatment-emergent high value if they have all normal or low values at all predose/baseline visits, followed by a value above the upper reference limit at any post-baseline visit. Participants with all normal or low values at baseline (no high values) will be included in the analysis of treatment-emergent high values.

The number and percent of participants meeting criteria for treatment-emergent abnormalities in vital signs at any time during study will be summarized. Treatment group comparisons will be performed using Fisher's exact test.

Table L displays the criteria used to define treatment emergent changes in vital signs and weight. The last column of the table displays the participant populations defined by baseline categories, the treatment-emergent categorical changes will be analyzed for each of those participant populations. The criteria generally consist of 2 parts, an absolute threshold and a change from baseline amount. The baseline and post-baseline definitions for vital signs analyses are in Table F

Table L displays the criteria for categorical changes of interest in vital signs. The last column of the table displays the participant populations defined by baseline categories. All vital signs data will be listed.

Document: CCI

Author: PPD

Version Number:

3.0

Version Date:

19May2023

CCI

Table L: Criteria for Categorical Changes of Interest in Vital Signs

Parameter	Direction	Criteria	Participants Population defined by Baseline Categories
Systolic BP (mm Hg) (sitting)	Low	≤90 and decrease ≥20	Low Population
	High	≥140 and increase ≥20	High Population
Diastolic BP (mm Hg) (sitting)	Low	≤50 and decrease ≥10	Low Population
	High	≥90 and increase ≥10	High Population
Pulse (bpm) (sitting)	Low	<50 and decrease ≥15	Low Population
	High	>100 and increase ≥15	High Population
Temperature (° F)	Low	<96° F and decrease ≥2° F	≥96°F
	High	≥101° F and increase ≥2° F	<101°F

Low Population definition: All participants who have values less than or equal to the low limit at all pre-baseline and baseline visits and at least one nonmissing postbaseline value.

High population definition: All participants who have values less than or equal to the high limit at all pre-baseline and baseline visits and at least one nonmissing postbaseline value.

Abbreviations: BP = blood pressure; bpm = beats per minute; F = degrees Fahrenheit; kg = kilograms; mm Hg = millimeters of mercury; PCS= Potentially Clinically Significant

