6.2. BASELINE AND POST-BASELINE

Unless otherwise specified, baseline is defined as the last non-missing measurement taken prior to reference start date (including unscheduled assessments). If the time of the measurement is collected, both the date and time will be used to determine the baseline. For example, if assessments collected at Visit 1 to Visit 3 (prior to dosing at Visit 3, and this can be confirmed

Document: CCI

Author: PPD

Version Number:

3.0

Version Date:

19May2023

CCI

by time of the assessment and dosing time), the last non-missing measurement at Visit 3 prior to the first dosing will be counted as baseline. In the case where the last non-missing measurement and the reference start date coincide and the time is not collected, that measurement will be considered pre-baseline if the assessment is planned per protocol to take place prior to the first dose of study medication.

Vital Parameters (Pulse, SBP, and DBP) as these are captured in triplicates. Baseline and post-baseline will be the mean of the triplicate value. If only one value available then that value is used, if 2 values are available then the 2 values are averaged and used for the value at that visit.

Adverse Events (AEs) and medications commencing on the reference start date will be considered post-baseline unless otherwise indicated based on available start date/time combination or collected eCRF information that identifies the individual event/medication as starting prior to first study medication administration.

For treatment emergent abnormal laboratory or vital signs, the baseline criterion considers all predose records, instead of the last record only. That is

- A treatment-emergent abnormal result is defined as a change from normal at all predose/baseline visits to abnormal at any time during the treatment period. Patients with all normal values at predose/baseline will be included in the analysis of treatment-emergent abnormal laboratory values
- A treatment-emergent high result is defined as a change from a value less than or equal to the high limit at all predose/baseline visits to a value greater than the high limit at any time during the treatment period. Patients with all normal or low values at predose/baseline (no high values) will be included in the analysis of treatment-emergent high laboratory values.

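### The SAP states two unreconciled event rules for a treatment-emergent vital-sign abnormality, a limit crossing alone and a threshold plus a minimum change, and does not say which is tabulated and tested

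*SAP*

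**What the plan says.** SAP 6.2 opens its rule with "For treatment emergent abnormal laboratory or vital signs, the baseline criterion considers all predose records". It then states the event: for the high direction, a participant with no high value before dosing who moves "to a value greater than the high limit at any time during the treatment period". No minimum change is required.

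SAP 20.3 introduces its bullets with "The baseline criteria for determining treatment-emergent vital sign abnormalities are". Each bullet then does two things. Its first sentence says who has a treatment-emergent value: for the high direction, no high baseline value, "followed by a value above the upper reference limit at any post-baseline visit". Its second sentence says who is in the denominator. Again there is no minimum change.

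After a sentence announcing the summary and Fisher's exact test, 20.3 continues: "Table L displays the criteria used to define treatment emergent changes in vital signs and weight". It adds: "The criteria generally consist of 2 parts, an absolute threshold and a change from baseline amount". Every row of Table L has both parts; systolic high is "≥140 and increase ≥20". The same section points to Table F for baseline, which is the maximum of Visits 1 to 3 for high values and the minimum for low values. Table L is also labelled as showing categorical changes of interest.

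Protocol 9.3.4.2 refers to criteria for treatment-emergent vital-sign abnormalities and to Fisher's test but does not define the criteria.

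**The concern.** One label, treatment-emergent, is attached to two event rules in the same section, and the sentence that sets up the table and the test sits between them. Two programmers could each follow the SAP and produce different incidence tables. If the choice is settled only after unblinding, it is open to being data-dependent. Vital signs are a named component of the safety objective and are compared between arms, so the reported incidences should follow from one stated rule.

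**Working it through.** **1. The two rules side by side**

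| | Limit-only (6.2; 20.3 bullets) | Two-part (20.3 text; Table L) |
|---|---|---|
| Event, high direction | above the upper reference limit | systolic ≥140 with a rise ≥20; diastolic ≥90 with a rise ≥10; pulse >100 with a rise ≥15 |
| Limits stated | none for vital signs | yes, by row |
| Minimum change | none | yes, in every row |

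**2. Examples, taking Table L's 140 as the limit**

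- Highest baseline 135, later value 142: above 140, so a limit-only event. The rise is 142 − 135 = 7, below 20, so not a two-part event.
- Highest baseline 118, later value exactly 140: not above 140, so not a limit-only event. It is at least 140 and the rise is 140 − 118 = 22, so it is a two-part event.

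The second example depends on the reference limit being 140, which the SAP does not say.

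**3. Size, under assumed distributions**

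The documents give no mean, SD or incidence for any vital sign, so there is no figure of the plan's own to reproduce.

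From the documents: vital signs at Visits 1, 3 and 6 (Protocol SoA); limits L and minimum changes d from Table L; baseline from Table F.

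Assumed, with no drug effect:
- systolic mean 118–122, between-person SD 9–12, visit-to-visit SD 6–10;
- diastolic mean 76–79, SDs 6–8 and 4–7;
- pulse mean 72, SDs 7–9 and 5–9.

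Model: Y = person mean + visit deviation, both normal; 2,000,000 simulated participants per scenario; blood pressure rounded to whole mm Hg. For the high direction, a participant is eligible if max(Y1, Y3) ≤ L. Among the eligible:
- A (limit-only) = P(Y6 > L)
- B(i) = P(Y6 meets the threshold and Y6 − max(Y1, Y3) ≥ d), the Table F baseline
- B(ii) = the same with Y6 − Y3, the last baseline

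The low direction mirrors this, with the bullets' denominator (no low baseline value).

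| | A | B(i) | A/B(i) | A/B(ii) |
|---|---|---|---|---|
| Systolic high | 1.0–6.1% | 0.04–1.6% | 3.2–40 | 1.8–10 |
| Systolic low | | | 2.1–30 | 1.4–7.7 |
| Diastolic high | 1.2–7.3% | 0.24–4.0% | 1.6–7.1 | 1.2–3.0 |
| Diastolic low | at most 0.49% | at most 0.38% | 0.9–3.7 | 0.7–1.9 |
| Pulse high | 0.04–0.98% | 0.01–0.49% | 1.7–11 | 1.3–4.3 |
| Pulse low | 0.31–2.66% | 0.03–1.15% | 2.1–16 | 1.5–5.6 |

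Ratios below 1 for low diastolic pressure arise because a value of exactly 50 counts under Table L but is not below 50. Temperature gives too few events for a useful ratio. Leaving the triplicate means unrounded makes the systolic and high-diastolic ratios larger, so the ranges are not bounds.

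One scenario in counts, high systolic pressure with mean 122 and SDs 12 and 8, per 575 eligible participants: about 25 events under A (25/575 = 4.3%), 3 under B(i) (0.5%) and 7 under B(ii) (1.2%). The ratios are 25/3 ≈ 8 and 25/7 ≈ 3.6. With 575 randomized, fewer would be eligible; the counts fall in proportion and the ratios stay.

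**4. The low-direction denominator**

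The bullets and Table F admit participants with no low baseline value. Table L's Low Population footnote admits those whose baseline values are all at or below the low limit. Read literally, the two groups share only participants exactly at the limit. Under the footnote, a systolic-low event needs a value of 90 − 20 = 70 or less. Table L's own temperature row follows the bullets' direction.

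**The case against.** The strongest defence is that the text already assigns roles. The bullets and 6.2 are introduced as baseline criteria, the inclusion sentences in 6.2 name only laboratory values, and 20.3 says that Table L supplies the definition. Since no vital-sign limits exist outside Table L, the limit-only rule cannot be programmed without borrowing half of Table L. The categorical-changes label also allows two separate analyses. Output templates mentioned in SAP section 8 are not among the public documents and may settle the matter.

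Much of this stands. It makes Table L the likelier intended event rule, and it is why a reader who infers outright incompatibility goes too far. It does not remove the conflict. The first sentence of each bullet defines the event, not the population, and SAP 20.2 uses nearly the same sentence as the laboratory event definition. If two roles or two analyses were meant, the SAP does not say so.

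Three further inferences are tempting and unsupported:
- That incidence differs several-fold across vital signs. No document gives an incidence, and under the assumptions low diastolic pressure is often near 1.
- That limit-only events are mostly measurement noise. This follows from assuming no drug effect, and says nothing about the trial's data.
- That the boundary differs, above the limit against at or above 140. This holds only if the unstated reference limit is 140.

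**Conclusion.** The concern holds as an unreconciled conflict between two stated event rules, not as a proven distortion of results. That the rules count different events follows from the text. How far the counts differ rests on assumed means and SDs, normality, one post-baseline visit and no drug effect. On that basis the gap is large for high systolic pressure, moderate for high diastolic pressure and small or absent for low diastolic pressure. Whichever rule is used applies to both arms, the comparisons carry no multiplicity control, and all vital-sign data are listed. The primary and key secondary analyses are untouched. The Low Population footnote is a firmer contradiction and needs no distributional assumption.

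**What to change.** In SAP 20.3, keep the bullets as the baseline-eligibility (denominator) rule only and delete their limit-only outcome sentence. State that the event tabulated and tested is the two-part Table L criterion, with change measured from the Table F baseline (maximum of Visits 1 to 3 for high, minimum for low). In SAP 6.2, limit the event definitions to laboratory tests. If the sponsor also wants a limit-only table, label it as a separate output and state its limits.

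At the same time, reconcile the Low Population footnote with the bullets' requirement of no low baseline value; otherwise making Table L the event rule leaves the low-direction analysis unusable. The mention of weight can be dropped, since Table L has no weight row.

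The cost is SAP wording, with matching programming specifications, before unblinding. The downside is lower reported incidences for most parameters than under the limit-only rule.

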Treatment emergent changes in blood pressure (average of the triplicate value)	Safety Analysis Set with normal blood pressure values at all non-missing baseline visits (with respect to direction being analyzed) and who have at least one post-baseline observation	Low: Minimum value from Visits 1-3 High: Maximum value from Visits 1-3	Low: Minimum value from Visits 3.01-6 High: Maximum value from Visits 3.01-6
Treatment emergent changes in pulse (average of the triplicate value)	Safety Analysis Set with normal pulse values at all non-missing baseline visits (with respect to direction being analyzed) and who have at least one post-baseline observation	Low: Minimum value from Visits 1-3 High: Maximum value from Visits 1-3	Low: Minimum value from Visits 3.01-6 High: Maximum value from Visits 3.01-6

- Abbreviations: ITT = intent-to-treat; forward; NA = not applicable; TEAE = treatment-emergent adverse event.
- Note: Visit 3.01 indicates the first unscheduled visit occurring after Visit 3 and prior to Visit 4.

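### The Table L footnote defines the blood pressure and pulse Low Population in the wrong direction, contradicting SAP 20.3, SAP 6.2, Table F and Table L's own temperature row; correct it before programming.

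*SAP*

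**What the plan says.** SAP 20.3 introduces its inclusion rules with "The baseline criteria for determining treatment-emergent vital sign abnormalities are". For the low direction the rule is: "Participants with all normal or high values at all predose/baseline visits (no low values) will be included in the analysis". The section then turns to Table L. It says the last column holds the populations and that "the treatment-emergent categorical changes will be analyzed for each of those participant populations". The same paragraph adds: "The baseline and post-baseline definitions for vital signs analyses are in Table F".

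Table F (SAP 6.2) gives the blood pressure population as "Safety Analysis Set with normal blood pressure values at all non-missing baseline visits (with respect to direction being analyzed" and the pulse population as "Safety Analysis Set with normal pulse values at all non-missing baseline visits (with respect to direction being analyzed". The text of 6.2 covers vital signs through its lead-in, "For treatment emergent abnormal laboratory or vital signs, the baseline criterion considers all predose records, instead of the last record only", and defines a treatment-emergent low as a fall from values at or above the low limit at all pre-dose visits.

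Table L gives two-part low criteria:

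- systolic BP ≤90 with a decrease ≥20;
- diastolic BP ≤50 with a decrease ≥10;
- pulse <50 with a decrease ≥15.

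For these three rows the population column says only Low Population, and the footnote is its sole definition: "Low Population definition: All participants who have values less than or equal to the low limit at all pre-baseline and baseline visits". The temperature row states its own population for the low direction, a baseline of 96 °F or above.

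**The concern.** A treatment-emergent low analysis should start with participants who are not low before dosing and count those who become low. The footnote starts with those who are low at every pre-dose visit. The High Population footnote has the same wording, with values at or below the high limit, and there the direction is right. Only the low line is reversed.

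The footnote cannot be dismissed as stray text, because 20.3 directs that the changes be analysed in the populations Table L names, and no other definition of Low Population exists. A programmer working from Table L would apply it. The low-BP and low-pulse rows would then show near-empty denominators and almost certainly no events, which a reader could take as reassurance. Vital signs belong to the safety objective (SAP Table B), and 20.3 plans a Fisher's exact comparison between arms.

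**Working it through.** The plan gives no figure to reproduce here; the question is one of definition.

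**1. The statements side by side (low direction)**

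| Source | Baseline requirement |
|---|---|
| Table L footnote (BP, pulse) | at or below the low limit at all visits |
| SAP 20.3 inclusion rule | no low value at any visit |
| SAP 6.2 definition | at or above the low limit at all visits |
| Table F (BP, pulse) | normal in the direction analysed |
| Table L temperature row | ≥96 °F |

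The footnote stands alone against the other four.

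**2. What an event would require**

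Take the low limit to be the Table L threshold (an assumption; see the objection). If every baseline value is at or below the limit, then whichever baseline value the change is taken from, post-baseline ≤ baseline − decrease ≤ limit − decrease:

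- systolic BP: 90 − 20 = 70
- diastolic BP: 50 − 10 = 40
- pulse: 50 − 15 = 35

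Enumerating whole-number baseline and post-baseline pairs from 20 to 220 gives the same three cut-offs. With the inequality reversed, an event can occur at the Table L threshold itself: systolic 90 from a baseline of 110 or more, diastolic 50 from 60 or more, pulse 49 from 64 or more.

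**3. Overlap of the two populations**

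Under the Table L cut-offs, no systolic or diastolic baseline value satisfies both the footnote and the 20.3 rule. For pulse the only such value is exactly 50 bpm (≤50, but not <50).

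**4. Size, under assumed distributions**

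The Schedule of Activities (Protocol 1.3) places pre-dose vital signs at Visits 1 and 3. The two baseline values were modelled as bivariate normal with correlation r, and probabilities were multiplied by 575, the planned minimum. With z = (limit − mean)/SD:

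- kept by the footnote = 575 × P(both ≤ z)
- kept by the 20.3 rule = 575 × [1 − 2P(one ≤ z) + P(both ≤ z)]

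Assumed ranges:

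| | Moderate grid | Wider grid |
|---|---|---|
| Systolic mean; SD | 115–125; 11–15 | 112–128; 10–16 |
| Diastolic mean; SD | 72–80; 8–10 | 70–82; 7–11 |
| Pulse mean; SD | 68–76; 9–11 | 66–78; 8–12 |
| r | 0.5–0.8 | 0.4–0.8 |

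Example, at the corner of the moderate grid with the most low baselines (systolic mean 115, SD 15): z = (90 − 115)/15 = −1.667. With r = 0.8 the footnote keeps 13.5. With r = 0.5 the 20.3 rule keeps 526.6.

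| Kept, of 575 | Systolic | Diastolic | Pulse |
|---|---|---|---|
| Footnote, moderate grid, at most | 13.5 | 3.2 | 14.5 |
| 20.3 rule, moderate grid, at least | 526.6 | 560.2 | 523.7 |
| Footnote, wider grid, at most | 26.5 | 9.2 | 29.0 |
| 20.3 rule, wider grid, at least | 489.7 | 538.4 | 483.5 |

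As shares, the footnote keeps at most 14.5/575 = 2.5% (moderate) or 29.0/575 = 5.0% (wider). The 20.3 rule keeps at least 523.7/575 = 91.1% or 483.5/575 = 84.1%.

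**5. Expected low events**

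These were simulated at the grid corners with one post-baseline visit, change taken from the minimum baseline value (as in Table F) and no treatment effect.

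| Maximum events per 575 | Systolic | Diastolic | Pulse |
|---|---|---|---|
| Footnote, moderate grid | 0.017 | 0.014 | 0.023 |
| Footnote, wider grid | 0.065 | 0.062 | 0.094 |
| 20.3 rule, moderate grid | 5.2 | 3.6 | 5.0 |
| 20.3 rule, wider grid | 11.4 | 9.5 | 11.8 |

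**The case against.** The best reply is that this is a one-word slip which the SAP already resolves. Section 20.3 states the right rule in its bullets and again by pointing to Table F, and the temperature row shows the intent. On that view the point is editorial. The argument goes further: safety is only described, all vital signs are listed, and the scheduled post-dose vital signs are at Visit 6 or early termination only. Even under the correct rule the moderate grid yields about five events at most. With 288 and 287 per arm, a 4–0 split gives a Fisher p of 0.06 to 0.12 and a 5–0 split 0.03 to 0.06, so the comparison says little either way.

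Much of this stands as a limit on severity. It does not remove the contradiction: the SAP gives no order of precedence, and 20.3 sends the analysis to the Table L populations as well as to Table F. The wider grid, or a real effect on blood pressure or pulse, would leave more to lose.

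Three narrower objections are fair:

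- A baseline pulse of exactly 50 is normal under Table L yet admitted by the footnote, so the exclusion of normal values is not quite total. Under 6.2, a BP value exactly at the limit is likewise both not low and admitted.
- No number is attached to the low limit in the footnote or to the lower reference limit in 20.3. Reading both as the Table L thresholds is an assumption. The reversal of direction does not depend on it; the 70, 40 and 35 cut-offs do.
- The means, SDs and correlations come from outside the documents. They indicate scale and are not evidence for the contradiction.

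**Conclusion.** The concern holds. The Low Population footnote is reversed, is the only definition of that term, and is tied to the analysis by the text of 20.3. Followed literally, it empties the low systolic, low diastolic and low pulse rows of nearly all participants with normal baseline values and makes an event almost impossible. The direction of the error and the lack of overlap (apart from boundary values) follow from the text. The 70, 40 and 35 cut-offs also need the low limit to equal the Table L threshold, and the participant and event counts rest on the assumed distributions. The consequence is confined to three rows of a descriptive safety table and can be repaired from existing data. It should be fixed, but it does not threaten the trial's main conclusions.

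**What to change.** Before programming and unblinding, replace the Low Population footnote with:

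> Low Population: all participants with no low value by the Table L threshold at any pre-baseline or baseline visit (systolic BP >90 mm Hg, diastolic BP >50 mm Hg, pulse ≥50 bpm) and at least one non-missing post-baseline value.

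This agrees with 20.3 and Table F, so no rule of precedence between them is needed.

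One tie with 6.2 remains: 6.2 treats a value equal to the low limit as not low, while the Table L BP criteria count 90 and 50 as low. The High Population has the same kind of tie at exactly 140 and 90. Aligning these boundaries in 6.2, 20.3 and Table L is a sensible optional tidy-up. In a check of the low BP boundary, using ≥ in place of > moved the denominator by 1 to 9 of 575 and expected low events by less than 0.1.

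The cost is one footnote, with no new data and no change to any other analysis.
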